4.2.2. Protocol for participants exhibiting potential for self-harm

If a participant discloses that they may do harm to themselves, we will follow up with the participant and report to PI. This will be indicated with a score of greater than 0 on Question 9 on the PHQ-9. We will then administer the Suicidality Severity Screener (SSW form), adapted from the Columbia-Suicide Severity Rating Scale (C-SSRS), by Posner, K., et al, and used in prior ALA-ACRC studies.

We will proceed as follows

Suicidal Severity Screener

You mentioned on some of the questions that you have thought about killing yourself. Tell me about those thoughts.

1. Have you been thinking about how you might kill yourself?
YES /NO
2. Have you had these thoughts and had some intention of acting on them?
YES /NO
3. Have you started to work out or worked out the details of how to kill yourself?
YES/ NO
4. Do you intend to carry out any plans you have?
YES/ NO
5. Do you have a current mental health provider?
If yes- when is your next appointment?

Risk will be determined as outlined below:

Mild Risk

If participant answers NO to questions 1, 2, 3, AND 4 of the SSW:

- Notify PI
- Provide resource guide, including suicide hotline number, with statement: *"It sounds like currently you have some thoughts about suicide but do not plan to go through with it. If you notice the thoughts become more frequent, or you want to talk with someone, please call this number."*
- If they have a provider, make sure there is an upcoming appointment scheduled to talk about their concerns. If they do not have a provider, indicate possible providers on resource sheet.
- Complete an adverse Event Report (UE) form documenting the outcome of this questionnaire and subsequent action taken.
- Contact the participant by phone 7 days after visit to confirm they are receiving follow up care. Update AE form with results of phone call.
- A letter will be mailed with resources if we are unable to reach them by phone, and this will be discussed with the study physician

Moderate Risk

If participant answers YES to questions 1 or 2 but not to questions 3 or 4 of the SSW:

- Notify study physician immediately
- Provide resource guide, including suicide hotline number, with statement: *"It sounds like currently you have some thoughts about suicide but do not plan to go through with it. If you notice the thoughts become more frequent, or you want to talk with someone, please call this number."*
- If they have a provider, make sure there is an upcoming appointment scheduled to talk about their concerns. If they do not have a provider, staff should strongly encourage them to contact the suicide hotline and/or one of the local providers listed to schedule a follow up call or appointment.
- Staff should encourage participants to contact the hotline or schedule an appointment before concluding the study visit.
- Complete an Adverse Event Report (AE) form documenting the outcome of the questionnaire and subsequent action taken.
- Contact the participant by phone 7 days after visit to confirm they are receiving follow up care. Update AE form with results of phone call.
- A letter will be mailed with resources if we are unable to reach them by phone, and this will be discussed with the study physician

Immediate Risk

If participant answers YES to questions 3 or 4 of the SSW:

- Notify study physician immediately
- Instruct participant to call PCP, 911, or appropriate crisis number and give participant resource guide highlighting 24-hr help lines.
 - If participant does not call for assistance, let them know you are obligated to report this to emergency services; walk participant to ER or call 911
- If concerned there is an immediate risk, walk the participant to the ER or call 911
- Complete a Serious Adverse Event Report (SR) form documenting the outcome of this questionnaire and subsequent action taken.
- Contact the participant by phone 7 days after visit to confirm they are receiving follow up care. Update SR form with results of phone call.

If unsure about the patient's risk, contact a study physician (preferably the PI) to notify them immediately and discuss action to take.

If patient is contacted and it is determined that they are not receiving follow up care/ it is not possible to reach the patient, contact the study physician immediately, who will contact their site's psychiatrist or licensed psychologist to discuss appropriate next steps.

FOR ALL SUICIDALITY RISK ASSESSMENTS:

Speak with a study doctor immediately and the study PI as soon as possible.

Assessment of Insomnia: sleep difficulties will be assessed by response to PHQ9 questions #3, if a participant scores ≥ 2 this will be discussed with the study physician (preferably the study PI) as soon as possible.

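### Section 4.2.2 reads the Mild-risk statement unchanged to Moderate-risk participants, so a reported intention to act goes unacknowledged and, in some cases, is contradicted

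*Combined protocol and SAP*

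**What the plan says.** A PHQ-9 item 9 score above 0 triggers a short suicidality screener (section 4.2.2). Two of its four risk questions matter most here. Question 2 asks: "Have you had these thoughts and had some intention of acting on them". Question 4 asks: "Do you intend to carry out any plans you have". Question 1 concerns thinking about a method, and question 3 concerns working out details.

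The Mild tier applies under this rule: "If participant answers NO to questions 1, 2, 3, AND 4 of the SSW". The Moderate tier applies under this one: "If participant answers YES to questions 1 or 2 but not to questions 3 or 4 of the SSW". YES to question 3 or 4 is Immediate risk.

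In both the Mild and the Moderate tier, staff hand over a resource guide and read the same two sentences: "It sounds like currently you have some thoughts about suicide but do not plan to go through with it", followed by "If you notice the thoughts become more frequent, or you want to talk with someone, please call this number".

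The staff actions do differ. In the Moderate tier the study physician is notified immediately, and a further step reads: "Staff should encourage participants to contact the hotline or schedule an appointment before concluding the study visit". For every suicidality assessment the plan adds: "Speak with a study doctor immediately and the study PI as soon as possible".

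**The concern.** The plan separates Moderate from Mild by the answers to questions 1 and 2 and steps up the staff actions to match. The words spoken to the participant do not step up. Someone who has just reported some intention of acting hears a summary that mentions only thoughts and says there is no plan to act. The advice to call is then conditional on the thoughts becoming more frequent or on wanting to talk. That is softer than the tier's own instruction to encourage contact before the visit closes.

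What is at stake is participant safety, not inference. Section 4.1.1 reports that the drug label warns of suicidality, and that suicidal ideation and behavior occurred in people with and without prior depression. A scripted response that passes over or denies a disclosure is a poor fit in that setting, even if it is rarely used.

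**Working it through.** No figure in the plan needs reproducing. The check compares the two statements and lists the answer patterns.

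**Statements.** The Mild and Moderate texts are identical character for character. Neither sentence refers to intention. No other wording is given for question 2 = YES.

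**Patterns.** Four YES/NO questions give 2^4 = 16 patterns. Requiring NO to questions 3 and 4 leaves 2^2 = 4; the other 16 - 4 = 12 are Immediate.

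| Answers to questions 1-4 | Tier | Fit of the statement |
|---|---|---|
| NNNN | Mild | Fits |
| YNNN | Moderate | No intention reported, so none is passed over |
| NYNN | Moderate | Omits the reported intention; may contradict it |
| YYNN | Moderate | Omits the reported intention; may contradict it |
| 12 patterns with YES to 3 or 4 | Immediate | This statement is not used |

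So 2 of the 3 Moderate patterns are affected. These are counts of patterns, not probabilities.

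**When omission becomes contradiction.** Question 2 is phrased in the past, so YES may describe an intention that has gone. For that person, NO to questions 3 and 4 agrees with the statement. Question 4, however, asks only about plans the person already has. A participant with present intent and no plan can truthfully answer NO to both questions 3 and 4, remain Moderate, and be told they do not plan to act.

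**Ceiling on occasions.** The visit table in section 2.9 schedules the depression questionnaire at all seven visits. Item 9 above 0 is an exclusion criterion (section 2.1.2). A participant who is later randomized therefore cannot have triggered the screener at V1, or at V2 if it is scored before randomization. That leaves V3 to V7, five visits, for 38 participants: 38 x 5 = 190 scheduled assessments. Screened people who are not randomized come on top, since section 4.2.1 covers them too; their number is not given.

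The 190 counts questionnaires, not screener triggers. The exclusions for major depressive disorder, past suicidal ideation or attempt, PHQ-9 of 15 or more and GAD-7 of 10 or more lower the expected frequency further. The documents give no rate for item 9 above 0 or for question 2 = YES.

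**The case against.** The strongest reply is that the statement merely restates the NO answers to questions 3 and 4, so it is accurate for many Moderate participants, and that not echoing question 2 is a matter of communication style. The first half stands: a reader might infer that the script contradicts everyone who answers YES to question 2, and the documents do not support that. The second half does not fully stand, because the wording of question 4 leaves room for present intent without a plan.

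A second reply is that the encounter is much more than the script. The screener opens by inviting the participant to talk about the thoughts. The physician is told at once, staff encourage contact before the visit ends, and staff unsure of the risk must call a study physician. Study drug is stopped (sections 2.10, 4.1.1 and 4.2.1). The 7-day call escalates to the site's psychiatrist or licensed psychologist if care is not in place or the person cannot be reached. Site-specific care plans exist but are not in the documents. All of this stands. A reader might infer that the plan fails to escalate such participants; it does escalate them. These steps limit the harm but do not correct the statement.

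Third, the screener was used in earlier network studies. The plan says this of the screener; it does not say the tier statements were tested.

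Fourth, if present intent without a plan is the worry, question 4 or the tier rule is the more direct target. That is fair. Changing either is a clinical classification decision, and the wording change does not depend on it.

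**Conclusion.** The point holds as a participant-safety wording issue. For the two Moderate patterns with question 2 = YES, the statement does not acknowledge the reported intention. For an unknown subset with present intent but no plan, it contradicts that intention.

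Few cases are expected in a trial of 38 with these exclusions, and there may be none. The tier, the reporting form, the follow-up steps and every analysis are unaffected. It would be too strong to call the change essential, or to treat the statement as all that such a participant hears. It is a worthwhile, low-cost improvement.

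The conclusion rests on reading question 4 literally, as limited to existing plans, and on there being no alternative wording in site plans that cannot be seen here.

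**What to change.** When question 2 = YES in the Moderate tier, use a separate statement that drops the clause about having no plan to act, acknowledges the intention, offers help making contact before the visit ends, and keeps the advice to call afterwards in a less conditional form. For example:

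> You told me you have had some intention of acting on these thoughts. We would like to help you contact this hotline or a provider before this visit ends. After today, please call this number at any time, especially if the thoughts or the intention return or become stronger.

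The last sentence matters: without it, the replacement would remove the script's only advice for the period after the visit. The wording also suits the visits that section 2.11 allows to be remote.

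Clear the text through the DSMB review foreseen in section 4.2; section 5 names a psychiatrist as the content expert for this board. Leave the Mild statement, the wording for YNNN, the tiers and the follow-up steps as they are.

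The cost is a form or protocol revision, DSMB and IRB handling, and brief retraining at seven sites. No visits, participants or analyses are added.

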2.9. Procedures

Sites conducting remote follow up visits must use a secure (password protected) zoom link or other secure online communication method. Participants who are followed up remotely, will complete some questionnaires over the phone and mail back the rest of the questionnaires to the site.

Outline of Study Visits							
Week	-1	0	2	6	12	18	24
Visit number	V1	V2	V3	V4	V5	V6	V7
Consent	•						
Baseline/interim history	•	•	•	•	•	•	•
Randomization		•					
Pill distribution†		•		•	•		
Pill distribution‡		•			•		
Review of paper/electronic diary cards		•	•	•	•	•	•
Pill Counts			•	•	•	•	•
Asthma Control	•	•	•	•	•	•	•
Anxiety/depression questionnaires	•	•	•	•	•	•	•
GSRS	•	•	•	•	•	•	•
QOL	•	•	•	•	•	•	•
Anthropometrics	•	•	•	•	•	•	•
Fasting Blood draw¥		•					•
Pregnancy test*	•	•	•	•	•	•	•
End of study questionnaire							•

† if dose frequency is every day since V3

‡ if dose frequency is every other day since V3

¥ conduct blood draw only if site permits it

*for women of child-bearing potential and participating in remote follow up participants will be mailed testing kit, and asked to send photo of result to coordinator

- Participants will be trained on how to perform peak expiratory flow at the study visit and sent home with asthma action plan.
- Asthma paper/electronic diary cards will be completed by participants throughout the study to record daily morning peak expiratory flow (PEF), daily asthma symptom scores, beta-agonist use, nocturnal asthma awakenings, and health care use.^{17,18} Diary data are used to identify episodes of poor asthma control and days with no asthma symptoms (asthma-free days).
- The Asthma Control Test (ACT) is a 4-week recall questionnaire that measures asthma control.¹⁹
- The Marks Asthma Quality of Life Questionnaire (Marks AQLQ) assesses asthma specific quality of life.²⁰
- The Asthma Symptom Utility Index (ASUI) is a 2-week utility-weighted asthma symptom questionnaire.²¹
- GI side effects will be assessed with the Gastrointestinal Symptom Rating Scale. This is a 15-item instrument with five subscales (reflux, diarrhea, constipation, abdominal pain and indigestion) that was originally developed to assess the symptoms associated with the most common GI disorders, and has previously been used to assess tolerability of medications. The five subscales of the questionnaire produce a mean score ranging from 1 (no discomfort) to 7 (very severe discomfort).²²

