2.11. Modifications due to COVID-19 pandemic

Due to the COVID-19 public health emergency, TRIM, will permit remote follow up of enrolled participants as of April, 6, 2020. Participants enrolled after re-opening of the study should be seen at in-person visit for V2 (randomization visit) and V7 (24 weeks), other visits can be conducted in-part or fully remotely. It is possible that research activities will face restrictions in the future or that a participant will prefer to do the V4-V6 remotely, so we will provide participants with a scale and tape measure to collect data for remote visits. All questionnaires can be conducted remotely prior to in-person visits for all visits. Participants who are followed up remotely, will complete some questionnaires over the phone and mail back the rest of the questionnaires to the site. Methacholine challenge tests and spirometry should not be conducted. Women of child-bearing potential and participating in remote follow up will be mailed testing kit, and asked to send photo of result to coordinator

3. Data analysis

The appropriateness of the human, technological and systems components of the data acquisition and management procedures will be analyzed including practicality of data acquisition, estimation of likely participant characteristic and outcome distributions, suitability and functionality of paper and electronic forms, and resources required for participants contact and follow up, and to anticipate rates for missing data.

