Anticipated % patients experiencing an event compared to placebo if treated for 24 weeks with roflumilast 500 mcg per day (based on data above):

- diarrhea (9.7%)
- nausea (11.1%)
- insomnia (2.8%)
- headache (9.6%)
- dizziness (2.9%)

The psychiatric risks of roflumilast treatment are mitigated through the monitoring and management of symptoms as described below.

Weight loss is considered to be an advantageous outcome in the population being studied. *If a participant loses ≥ 10% of baseline weight during the course of the trial, this will be discussed with the study physician (preferably the study PI) as soon as possible.*

The GSRS will be used primarily to monitor GI side-effects, if a participant scores ≥ 6 on any item (indicative of severe or very severe discomfort), this will be discussed with the study doctor immediately, and the study PI as soon as possible.

The potential for drug interactions with roflumilast is mitigated through excluding participants on medications known to interact with roflumilast. We will exclude participants with uncontrolled anxiety and depression, and suicidal ideation, and screen for these at every visit, we will discontinue the patient from drug treatment if they develop these symptoms (threshold as defined in eligibility criteria). Plans for dealing with elevated symptoms of depression, anxiety and self-harm are outlined below.

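### The immediate-risk suicide step in section 4.2.2 is not reconciled with remote visits, and no stated step confirms where a remote participant is

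*Combined protocol and SAP*

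**What the plan says.** Section 2.11 permits remote follow-up because of the pandemic. Participants enrolled after re-opening are to attend V2 and V7 in person, and "other visits can be conducted in-part or fully remotely". It adds that "All questionnaires can be conducted remotely prior to in-person visits for all visits".

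The schedule in section 2.9, headed "Outline of Study Visits", lists the anxiety and depression questionnaires at all seven visits. Section 4.1.1 says of uncontrolled anxiety, depression and suicidal ideation that staff will "screen for these at every visit".

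Section 4.2.2 applies when PHQ-9 Question 9 scores above 0. A short screener then sorts the participant into mild, moderate or immediate risk. At moderate risk, "Staff should encourage participants to contact the hotline or schedule an appointment before concluding the study visit". At immediate risk, staff notify the study physician, "Instruct participant to call PCP, 911, or appropriate crisis number" and hand over a resource guide. If the participant does not call, staff say that they must report this to emergency services and "walk participant to ER or call 911". The same pair of actions is given again for the case where staff themselves judge the risk to be immediate. Section 4.2.2 has no branch for a remote visit.

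**The concern.** The remote-visit rules in sections 2.9 and 2.11 cover the video link, the return of questionnaires, scales and tape measures, and pregnancy kits. They do not touch the self-harm procedure. A reader who follows section 4.2.2 as written at a remote visit meets a final step that names two actions. One needs the participant in the building. The other needs to know where the participant is.

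The stake is participant safety. Section 4.1.1 reports that suicidal ideation and behavior, including completed suicides, were seen with this drug in people with and without previous depression. The step at issue is the last one in the sequence and is reached only after the participant has not called for help.

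**Working it through.** There is no sample size, power or event figure to reproduce. The check is a count of visits and a step-by-step reading.

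**1. How many visits may be remote**

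Inputs: seven visits, V1 to V7 (section 2.9); two to be in person, V2 and V7, for participants enrolled after re-opening (section 2.11).

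- All visits: 7 − 2 = 5 (V1, V3, V4, V5, V6); 5/7 = 71%.
- After randomization: V3 to V7 is 5 visits; 5 − 1 (V7) = 4; 4/5 = 80%.
- Narrower reading: section 2.11 also mentions a participant preferring V4 to V6 remotely. Counting only those gives 3/7 = 43% overall and 3/5 = 60% after randomization. The sentence that sets the rule refers to the other visits without limit, so 5 and 4 are the better counts.
- Questionnaires: because they may be done remotely ahead of in-person visits too, the PHQ-9 may be given remotely at any of the 7 visits.

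**2. Which steps of section 4.2.2 work at a remote visit**

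| Tier | Step | By phone or video? |
|---|---|---|
| All | Contact a study doctor or PI | Yes |
| All | Hand over the resource guide | Needs another route |
| Mild, moderate | Read the statement, check for an appointment, encourage contact with help | Yes |
| All | Complete the event form, phone at 7 days | Yes |
| Immediate | Tell the participant to call for help | Yes |
| Immediate | Staff walk the participant to the ER | No |
| Immediate | Staff call 911 | Yes, but depends on knowing the location |

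**3. Whether the location is established**

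Section 2.9 requires a secure link. Neither it nor section 2.11 states that current location or a call-back number is confirmed when a remote contact begins, and section 4.2.2 adds no such step. Mailed pregnancy kits and resource letters imply a postal address on file, and the follow-up calls imply a phone number. A postal address need not be where the person is during the visit. The staff call comes after the participant has not called for help, which is a poor moment to begin asking for a location.

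**4. A related conflict on timing**

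Section 4.2.1 has staff tabulate and review PHQ-9 and GAD-7 scores before the visit ends for that participant. Sections 2.9 and 2.11 let remote participants complete some questionnaires by phone and post back the rest, without saying which. The PHQ-9 is not excluded from the posted group, so a positive Question 9 could be seen only after the visit.

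**The case against.** The strongest case on the other side is that section 4.2.2 already contains actions that work remotely. It notifies the physician at once, tells the participant to call emergency or crisis services, and gives staff the option of calling 911. Section 4.2.1 also invokes a site-specific plan for participants who reach the exclusion thresholds, which under section 2.1.2 include a Question 9 score above 0. That plan and the remote-visit forms are not in the documents and may deal with location. The trial is a 38-person pilot that excludes people with current ideation or a history of ideation or attempt, and the counts above show what is permitted, not what is expected.

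Much of this stands, and it rules out several stronger readings that a reader might infer:

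- **That the moderate-risk steps also assume presence.** They do not. They are spoken steps, and only delivery of the guide needs another route.
- **That the participant's location is never recorded.** The documents are silent on location during a remote contact, but an address on file is implied.
- **That the whole emergency procedure fails remotely.** It does not. One staff action is lost and the other may be slower.
- **That exactly 4 of the 5 post-randomization Question 9 screens are affected.** That figure counts visits. Questionnaires may be remote even around V2 and V7, so it does not describe the screens.
- **That suicidality is monitored more closely than anything else.** The GSRS, asthma control and quality-of-life measures share the same every-visit schedule.

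What the objection does not remove is the gap in the text. Nothing in the protocol requires the site-specific plan to address remote visits, and the staff 911 call still depends on a location that no stated step confirms.

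**Conclusion.** The point holds in a limited form. For participants enrolled after re-opening, 5 of 7 visits, including 4 of the 5 after randomization, may be fully remote. At such a visit, one of the two immediate-risk staff actions is unavailable and the other may be delayed. The mild- and moderate-risk steps can be carried out remotely apart from handing over the guide. Separately, the rule that scores are reviewed within the visit conflicts with the mail-back of unspecified questionnaires.

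This should be corrected because it concerns safety and costs little. It does not touch the trial's analysis. The conclusion assumes that the rule on other visits covers V1 and V3 as well as V4 to V6, and that no document outside those reviewed already confirms location. The documents do not allow an estimate of how many immediate-risk events would arise at remote visits, and none is offered.

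**What to change.** - In sections 2.9 and 2.11, have staff record the participant's current physical location and a call-back number at the start of each remote contact, before the PHQ-9 is given. This is visit logistics and sets no clinical rule.
- Reconcile the immediate-risk step in section 4.2.2 with section 2.11 so that it can be carried out at a remote visit. The clinical content belongs to the investigators, the site psychiatrist or psychologist, and the DSMB, to whose review section 4.2 already submits the plan. The spoken steps in the mild and moderate tiers need no rewrite.
- Reconcile the score-review rule in section 4.2.1 with the mail-back of questionnaires in sections 2.9 and 2.11, making clear where the PHQ-9 falls.

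The cost is protocol wording, a short added form field and a little time at each remote contact.
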